9.2.4.2 Methylation Profiling

DNA Methylation studies will be performed at the Breast Cancer Research Laboratories at Johns Hopkins under the direction of [name]. We expect that over 70% of patients will have circulating DNA at baseline. QM-MSP studies will be done on DNA extracted from serum obtained from each subject. Primers and probes for QM-MSP analysis have been designed to specifically amplify hypermethylated promoter sequences of Cyclin D2, RAR-beta, APC-1, Twist, RASSF1A, HIN-1, and ER-alpha. PCR will be performed in separate wells for each primer/probe set. Fluorogenic PCR amplification will be carried out using a 7,900 Sequence detector (Perkin-Elmer Applied Biosystems) as previously described.

10. STUDY CALENDAR AND VISIT SCHEDULE

Baseline evaluations are to be conducted within 3 weeks prior to start of protocol therapy.

For the first cohort:

Procedure	Pre-study	Week 1		Week 2		Week 3		Week 4		Week 5		Surgery ^a	Off treatment
		D1	D4-7	D8	D9-14	D15	D16-21	D22	D23-28	D29	D30-32		
Minimum treatment						Optional							
Treatment:													
Entinostat		A		A		A		A		A			
Anastrozole/Tamoxifen			B	B	B	B	B	B	B	B	B		
Clinical assessment:													
Informed consent	X												
Demographics	X												
Medical history	X												
Current medications	X	X		X		X		X		X		X	X
Physical exam	X	X		X		X		X		X		X	X
Vital signs	X	X		X		X		X		X		X	X
Height	X												
Weight	X	X		X		X		X		X		X	X
Performance status	X	X		X		X		X		X		X	X
Adverse event evaluation		X		X		X		X		X		X	X
Tumor measurement ^b	X	X		X		X		X		X		X	
Laboratory test:													
CBC w/diff, plts	X	X		X		X		X		X		X	X
Chemistries ^c	X	X		X		X		X		X		X	X
PT/INR, PTT	X											X	
Electrocardiogram	X												
Pregnancy test ^g	X												
Correlative studies (Research procedures):													
Pharmacokinetic study													
• Pilot phase, stage 1		X ^d				X ^d							
• Stage 2		X ^e				X ^e							
Methylation profile		X ^f										X ^f	
Tumor sample	X											X	

A: Entinostat: as per appropriate dose level PO weekly on day 1, 8, 15, 22 and 29 ± 2 days. Preferably 22 days.

B: Anastrozole for postmenopausal women: 1 mg PO daily starts on day 4 and continue until the day of definitive surgery (lumpectomy or mastectomy).

Tamoxifen for premenopausal women: 20 mg po daily starts on day 4 and continue until the day of definitive surgery (lumpectomy or mastectomy).

a: Within 6 days (preferably within 3 days) after the last dose of entinostat.

b: Tumor measurement: clinical tumor size, character, mobility, and location of the breast mass.

c: Chemistries: sodium, potassium, chloride, bicarbonate, BUN, creatinine, glucose, total bilirubin, calcium, total protein, albumin, AST (SGOT), ALT (SGPT), alkaline phosphatase, LDH, uric acid, phosphorus, and magnesium

d: Day 1: Prior to starting treatment
30 minutes after the first dose of entinostat

Day 15 (±1 day): BEFORE entinostat
30 minutes AFTER entinostat

e: Day 1: Prior to starting treatment

Day 15 (±1 day): BEFORE entinostat

f: Day 1: Prior to starting treatment

The day of definitive surgery (lumpectomy or mastectomy)

g: Serum or urine pregnancy test should be performed within 7 days prior to registration in women of childbearing potential

NOTE: Visit Windows ± 2 days

For the second cohort:

Procedure	Pre-study	Week 1		Week 2		Week 3		Week 4		Week 5		Continue until disease progression ^h	Off treatment
		D1	D4-7	D8	D9-14	D15	D16-21	D22	D23-28	D29	D30-32		
Treatment:													
Entinostat		A		A		A		A		A			
Anastrozole/Tamoxifen			B	B	B	B	B	B	B	B	B		
Clinical assessment:													
Informed consent	X												
Demographics	X												
Medical history	X												
Current medications	X	X		X		X		X		X			X
Physical exam	X	X		X		X		X		X			X
Vital signs	X	X		X		X		X		X			X
Height	X												
Weight	X	X		X		X		X		X			X
Performance status	X	X		X		X		X		X			X
Adverse event evaluation		X		X		X		X		X			X
Tumor measurement for palpable or visible tumors ^b	X	X		X		X		X		X			
Correlative studies (Research procedures):													
CBC w/diff, plts	X	X		X		X		X		X			X
Chemistries ^c	X	X		X		X		X		X			X
PT/INR, PTT	X												
Electrocardiogram	X												
Pregnancy test ^g	X												
Pharmacokinetic study													
• Pilot phase, stage 1		X ^d				X ^d							
• Stage 2		X ^e				X ^e							
Methylation profile		X ^f								X ^f			
Biopsies	X									X ^a			

A: Entinostat: as per appropriate dose level PO weekly until disease progression.

B: Anastrozole: 1 mg PO daily starts on day 4 and continue until disease progression.

Tamoxifen for premenopausal women: 20 mg po daily starts on day 4 and continue until disease progression.

- a: The post-treatment biopsy (biopsy#2) will be performed after a minimum of 15 days and a maximum of 29 days of treatment, but preferably close to 29 days. The post-treatment biopsy must take place within 6 days (preferably within 3 days) after the last dose of entinostat.
- b: Tumor measurement for palpable or visible tumor: clinical tumor size, character, mobility, and location of the breast mass. Restaging scans will be performed every 6 weeks while on treatment.
- c: Chemistries: sodium, potassium, chloride, bicarbonate, BUN, creatinine, glucose, total bilirubin, calcium, total protein, albumin, AST (SGOT), ALT (SGPT), alkaline phosphatase, LDH, uric acid, phosphorus, and magnesium
- d: Day 1: Prior to starting treatment
30 minutes after the first dose of entinostat
Day 15 (±1 day): BEFORE entinostat
30 minutes AFTER entinostat
- e: Day 1: Prior to starting treatment
Day 15 (±1 day): BEFORE entinostat
- f: Day 1: Prior to starting treatment
The day of post-treatment biopsy
- g: Serum or urine pregnancy test should be performed within 7 days prior to registration in women of childbearing potential

h: After the post-treatment biopsy, treatment will be continued until disease progression. Restaging scans will be performed every 6 weeks while on treatment. Follow up visits after the post-treatment biopsy will be every 4 weeks or at physician's discretion.

NOTE: Visit Windows \pm 2 days

VISIT SCHEDULE

The study consists of a maximum 21-day (3 weeks) screening phase prior to registration, start of study drug administration within 3 business days of registration. The follow-up phase will last 30 days after the last dose of study medication or until death, whichever occurs first.

10.1 Screening

Each potential patient will be screened before the start of the study to determine her eligibility for participation. These tests are to be conducted within 3 weeks prior to study registration. The following procedures will be performed:

- Informed consent (signed and dated by patient)
- Medical history and demographics
- Inclusion/Exclusion Criteria
- Concomitant medications and treatments will be recorded from 1 month prior to the start of study treatment.
- Physical examination including examination of major body systems, height, body weight, ECOG performance status, and vital signs (temperature, blood pressure, heart rate, respiratory rate)
- Clinical tumor assessment by a breast examination including clinical tumor size, character, mobility, and location of the breast mass. The patient will be examined by one of the treating investigators or his/her designee at each specified time point and after the final dose of treatment.
- Laboratory studies: CBC with diff; chemistries including sodium, potassium, chloride, bicarbonate (HCO_3^- or CO_2), BUN, creatinine, glucose, total bilirubin, calcium, total protein, albumin, AST (SGOT), ALT (SGPT), alkaline phosphatase, LDH, uric acid, phosphorus, and magnesium
- Coagulation study: PT with INR and PTT
- 12-lead electrocardiogram (ECG)
- Collection of tumor sample: Paraffin blocks and/or unstained slides

10.2 Registration

Registration will take place once the consented patient has completed the necessary screening procedures and is deemed eligible for study entry by the investigator or designee. Each registered patient will be assigned a unique identification number. Treatment should begin within 3 business days after registration. Please see registration process in more detail in section 4.2.

10.3 Study Days

The period called "Study Days" begins when the patient receives the initial dose of entinostat (Week 1 Day 1). Assessments are scheduled once a week with a visit window of \pm 2 day until the time of definitive surgery (lumpectomy or mastectomy) or the post-treatment biopsy. However, this may be repeated more often, as clinically indicated. A maximum 2-week delay for resolution of study drug-related toxicities is allowed. A patient should be discontinued from the study if a greater than 2-week delay occurs.

Week 1 Day 1

On Week 1 Day 1 only, the required assessment may be omitted if an acceptable screening assessment was performed within 3 days prior to Week 1 Day 1. Week 1 Day 1 is dictated by the day the patient receives the first dose of entinostat.

- Assessment of Concomitant Treatments including medication use

- Physical examination including examination of major body systems, height, body weight, ECOG performance status, and vital signs (temperature, blood pressure, heart rate, respiratory rate)
- Clinical tumor assessment by a breast examination including clinical tumor size, character, mobility, and location of the breast mass.
- Laboratory studies: CBC with diff; chemistries including sodium, potassium, chloride, bicarbonate, BUN, creatinine, glucose, total bilirubin, calcium, total protein, albumin, AST (SGOT), ALT (SGPT) , alkaline phosphatase, LDH, uric acid, phosphorus, and magnesium
- Study Drug Administration, and Drug Accountability
- Methylation profile study
- Pharmacokinetic study:
 - Pilot phase and stage 1 patients
 - Prior to the first dose of entinostat
 - 30 minutes after the first dose of entinostat
 - Stage 2 patients
 - Prior to the first dose of entinostat
- Administration of entinostat as per appropriate dose level orally

Week 3 Day 15

Day 15 after the first dose of entinostat.

- Assessment of Concomitant Treatments including medication use
- Physical examination including examination of major body systems, height, body weight, ECOG performance status, and vital signs (temperature, blood pressure, heart rate, respiratory rate)
- Clinical tumor assessment by a breast examination including clinical tumor size, character, mobility, and location of the breast mass.
- Laboratory studies: CBC with diff; chemistries including sodium, potassium, chloride, bicarbonate, BUN, creatinine, glucose, total bilirubin, calcium, total protein, albumin, AST (SGOT), ALT (SGPT) , alkaline phosphatase, LDH, uric acid, phosphorus, and magnesium
- Study Drug Administration, and Drug Accountability
- Pharmacokinetic study:
 - Pilot phase and stage 1 patients
 - Prior to the day 15 dose of entinostat
 - 30 minutes after the day 15 dose of entinostat
 - Stage 2 patients
 - Prior to the day 15 dose of entinostat
- Administration of entinostat as per appropriate dose level orally

Day 8, 22, and 29 after the first dose of entinostat

- Assessment of Concomitant Treatments including medication use
- Physical examination including examination of major body systems, height, body weight, ECOG performance status, and vital signs (temperature, blood pressure, heart rate, respiratory rate)
- Clinical tumor assessment by a breast examination including clinical tumor size, character, mobility, and location of the breast mass.
- Laboratory studies: CBC with diff; chemistries including sodium, potassium, chloride, bicarbonate, BUN, creatinine, glucose, total bilirubin, calcium, total protein, albumin, AST (SGOT), ALT (SGPT) , alkaline phosphatase, LDH, uric acid, phosphorus, and magnesium
- Study Drug Administration, and Drug Accountability
- Administration of entinostat as per appropriate dose level orally

For the first cohort:

Surgery day

The definitive surgery (i.e. lumpectomy or mastectomy) should be performed within 6 days (preferably within 3 days) after the last dose of entinostat.

- Assessment of Concomitant Treatments including medication use
- Physical examination including examination of major body systems, height, body weight, ECOG performance status, and vital signs (temperature, blood pressure, heart rate, respiratory rate)

- Clinical tumor assessment by a breast examination including clinical tumor size, character, mobility, and location of the breast mass.
- Laboratory studies: CBC with diff; chemistries including sodium, potassium, chloride, bicarbonate, BUN, creatinine, glucose, total bilirubin, calcium, total protein, albumin, AST (SGOT), ALT (SGPT) , alkaline phosphatase, LDH, uric acid, phosphorus, and magnesium
- Coagulation study: PT with INR and PTT
- Collection of tumor sample: Paraffin blocks and/or unstained slides
- Methylation profile study

For the second cohort:

The post-treatment biopsy (biopsy#2) day

The post-treatment biopsy (biopsy#2) will be performed after a minimum of 15 days and a maximum of 29 days of treatment, but preferably close to 29 days. The post-treatment biopsy must take place within 6 days (preferably within 3 days) after the last dose of entinostat.

- Assessment of Concomitant Treatments including medication use
- Physical examination including examination of major body systems, height, body weight, ECOG performance status, and vital signs (temperature, blood pressure, heart rate, respiratory rate)
- Clinical tumor assessment by a breast examination including clinical tumor size, character, mobility, and location of the breast mass.
- Laboratory studies: CBC with diff; chemistries including sodium, potassium, chloride, bicarbonate, BUN, creatinine, glucose, total bilirubin, calcium, total protein, albumin, AST (SGOT), ALT (SGPT) , alkaline phosphatase, LDH, uric acid, phosphorus, and magnesium
- Coagulation study: PT with INR and PTT
- Collection of tumor sample: Paraffin blocks and/or unstained slides
- Methylation profile study

After the post-treatment biopsy, treatment will be continued until disease progression.

- Restaging scans will be performed every 6 weeks while on treatment.
- Follow up visits after the post-treatment biopsy will be every 4 weeks or at physician's discretion.

10.4 End of Study (Treatment) / Withdrawal

All patients must continue to be observed for 30 days after the last dose of study medication or until death; whichever occurs first. At the end of the study treatment, the following procedures should be performed within 4 weeks.

- Assessment of Concomitant Treatments including medication use
- Physical examination including examination of major body systems, height, body weight, ECOG performance status, and vital signs (temperature, blood pressure, heart rate, respiratory rate)
- Laboratory studies: CBC with diff; chemistries including sodium, potassium, chloride, bicarbonate, BUN, creatinine, glucose, total bilirubin, calcium, total protein, albumin, AST (SGOT), ALT (SGPT) , alkaline phosphatase, LDH, uric acid, phosphorus, and magnesium

11. MEASUREMENT OF EFFECT

For the purposes of this study, patients should be reevaluated weekly until the definitive surgery.

11.1 Pathologic Response Determination

Pathological response in the breast, and when appropriate, in the axilla will be assessed.

11.1.1 Primary Endpoint Definitions for Ki67 and ER Expression

For the primary endpoints, pathological response for Ki67 and ER expression will be assessed in the primary breast tumor. As per the updated guideline from the American Society of Clinical Oncology (ASCO) and Colleges of

American Pathologists (CAP) published in June 2010, the recommended ER positivity is at least 1% positive tumor nuclei in the tumor samples.

- Ki67: $\geq 50\%$ reduction in Ki67 after treatment with entinostat and anastrozole.
- ER: $\geq 1\%$ staining of ER is considered a positive result.

11.1.2 Pathologic Response

- Pathologic Complete Response (pCR): No viable invasive cancer in pathologic specimen, as determined by histological examination. We will report whether in situ disease only was present in the specimen versus no disease. We will also report for each woman whether she had a pCR in the breast only, in the lymph nodes only, or in both.
- Nodal Disease: We will report the number of women who had positive lymph node prior to starting study drugs, or at the time of surgery: 0, 1-3, 4-10, or >10 lymph nodes.

11.2 Clinical Response Determination

Clinical response in the breast will be evaluated, and when appropriate, in the axilla, infraclavicular, supraclavicular regions, and skin. At the time of study enrollment, patients will have a breast examination. Physical examination findings will be documented including clinical tumor size, character, mobility, and location of the breast mass. In addition, T4 features must be described. The patient will be examined by one of the treating investigators or his/her designee at each specified time point and at the time of the surgery.

11.2.1 Endpoint Definitions for Clinical Response (UICC criteria)

- Complete response (cCR) in the breast on physical exam will be defined as the absence of any palpable abnormality: i.e., no skin or breast thickening, mass, or associated skin or nipple changes. CR will be recorded separately for the breast and axilla.
- Partial response (cPR) in the breast will be defined as a 50% or greater decrease in the product of bipерpendicular diameters as measured with a ruler, compared with the prechemotherapy measurement.
- Stable disease (cSD) in the breast will be defined as palpable disease which does not fit the definition of PR or PD.
- Progressive disease (cPD) will be defined as an increase in the product of bipерpendicular diameters of 25% or greater compared to the original measurement.
- Inevaluable disease (cID) is defined as breast cancer that is not palpable in two dimensions.

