 - Total bilirubin within normal institutional limits
 - AST(SGOT)/ALT(SGPT) ≤ 2.5 x institutional upper limit of normal
 - Creatinine within normal institutional limits or creatinine clearance ≥ 60 mL/min/1.73 m² for patients with creatinine levels above institutional normal

Additional Inclusion Criteria for the First cohort:

- 3.1.11 Unresected operable breast cancer that meets the following clinical stages (see Appendix B):
 - T1b, T1c, or T2
 - N0 or N1
 - M0 (No distant metastasis)

Additional Inclusion Criteria for the Second cohort:

- 3.1.12 Unresectable, inoperable, recurrent local-regional breast cancer or
- 3.1.13 Metastatic (stage IV) breast cancer
- 3.1.14 Patients must have measurable or evaluable disease (i.e. ascites or pleural/pericardial effusion). Patients with bone metastatic only will be excluded.
- 3.1.15 Patients must not have rapidly progressive disease, extensive visceral involvement, or any high risk characteristics that are not appropriate for this treatment as per investigator's discretion.
- 3.1.16 Patients must receive at least one prior line of chemotherapy but not more 2 prior chemotherapy regimens for stage IV breast cancer. Prior chemotherapy in the adjuvant and /or neoadjuvant setting is permitted. However, patients must have finished chemotherapy at least 2 weeks prior to enrollment.
- 3.1.17 Patients must have an accessible tumor lesion from which a fine needle aspirate or preferably a core biopsy specimen can be obtained. Patients with FNA only samples are allowed in this cohort. Ascites or pleural/pericardial effusion alone is not sufficient.

- 3.1.18 Patients must be willing to provide consents for 2 research biopsies. However, the pretreatment biopsy can be omitted in patients who have recent biopsy but have not been started on breast cancer treatment within 12 weeks prior to the registration and there is adequate tumor tissue sample as per section 3.1.9.

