5. TREATMENT PLAN

5.1 Agent Administration

Treatment will be administered on an outpatient basis. Reported adverse events and potential risks for anastrozole and entinostat are described in Section 7. Appropriate dose modifications for entinostat and anastrozole are described in Section 6. No investigational or commercial agents or therapies other than entinostat, anastrozole, and tamoxifen may be administered with the intent to treat the patient's malignancy.

In the first cohort:

- Treatment will be continued for a minimum of 15 days and a maximum of 29 days. If clinically acceptable, treatment should be preferably continued for 22 days prior to the definitive surgery.
- Anastrozole will be administered continuously starting on day 4 at a fixed dose of 1 mg oral once daily.
- In patients who are not postmenopause as defined by any of the following criteria, tamoxifen will be administered continuously instead of anastrozole starting on day 4 at a fixed dose of 20 mg oral once daily.

Postmenopausal as defined by any of the following criteria:

- Age \geq 60
- Age < 60 with amenorrhea > 12 months and an intact uterus and an FSH and estradiol level within the postmenopausal range by institutional laboratory parameters.
- Age < 60 with previous hysterectomy must have FSH and estradiol level within the postmenopausal range by institutional laboratory parameters.
- Any age having undergone bilateral oophorectomy
- Entinostat will be administered at the assigned dose once a week (on day 1, 8, 15, 22, and 29) until the definitive surgery. Entinostat should be taken with a meal after the first two or three bites.
 - The initial starting dose for entinostat is 5 mg oral weekly. Dose de-escalation to 3 mg/week is permitted in the pilot phase if dose limiting toxicity is observed as defined in section 5.2.1.
 - Dose level for entinostat in phase II part of this study will be determined after the pilot phase is completed.

In the second cohort:

1. Pretreatment biopsy (biopsy#1) will be performed within 3 weeks after registration. However, the pretreatment biopsy can be omitted in patients who have recent biopsy but have not been started on breast cancer treatment within 12 weeks prior to the registration and there is adequate tumor tissue sample as per section 3.1.9.

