5.6 Postoperative Treatments

5.6.1 Chemotherapy

It is recommended that postoperative chemotherapy be administered. The adjuvant chemotherapy regimen is at the discretion of the treating physicians.

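### Section 11.2.1 scores clinical partial response against an undefined prechemotherapy size, which in the second cohort, read literally, predates study entry and can credit earlier shrinkage to study drug

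*Combined protocol and SAP*

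**What the plan says.** All references are to the combined protocol and SAP.

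- **cPR (11.2.1):** a "50% or greater decrease in the product of" the two perpendicular diameters, "compared with the prechemotherapy measurement".
- **cPD (11.2.1):** an increase in the same product "of 25% or greater compared to the original measurement". Neither reference measurement is defined anywhere.
- **Treatment (5.1):** "No investigational or commercial agents or therapies other than entinostat, anastrozole, and tamoxifen may be administered" with anticancer intent. The regimen contains no chemotherapy.
- **Prior chemotherapy (3.1):** 3.1.7, listed as a general criterion, bars it for the current cancer. For the second cohort 3.1.16 says "Patients must receive at least one prior line of chemotherapy", with an upper limit of two regimens for stage IV disease, finished at least 2 weeks before enrolment.
- **Later chemotherapy, first cohort (5.6.1):** "It is recommended that postoperative chemotherapy be administered".
- **Baseline examination (11.2 and 10):** "At the time of study enrollment, patients will have a breast examination", and "Baseline evaluations are to be conducted within 3 weeks prior to start of protocol therapy". Both calendars in Section 10 schedule tumour measurement at pre-study and on day 1. In the second cohort this covers palpable or visible tumours only.
- **Use of the endpoint:** secondary objective 3 (1.2) concerns clinical and pathological response to the preoperative combination. Section 12.4 estimates the rates in all eligible patients, with no restriction by cohort.

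**The concern.** A response definition should measure change from the start of the treatment under study. The cPR reference is named after a treatment that the study does not give. For patients who received that treatment before enrolment, the name points to a time before the study.

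Shrinkage achieved by earlier chemotherapy could then count towards response to entinostat plus endocrine therapy. With no control arm, nothing in the design would reveal the error. In addition, if the cPD reference means the study baseline, response and progression are judged from different starting points. One patient could then satisfy both definitions, and 11.2.1 has no rule on which prevails.

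**Working it through.** The plan states no figure that depends on this definition, so there is none to reproduce. The check has three parts.

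**1. What the cPR reference means in each cohort**

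| | First cohort | Second cohort |
|---|---|---|
| Chemotherapy before enrolment | None for the current cancer (3.1.7) | Required (3.1.16) |
| Chemotherapy after study drug | Recommended after surgery (5.6.1) | Not specified |
| Is the enrolment examination prechemotherapy? | Yes | No |
| Literal cPR reference | Enrolment examination qualifies, but so does every later preoperative examination | A size from before the earlier chemotherapy, so before study entry |
| Earlier chemotherapy shrinkage to carry over | None | Possible |

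**2. On-study change needed for cPR under the literal reading**

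Set the prechemotherapy product to 100. Let s be the fraction lost to earlier chemotherapy. The documents give no value for s, so it is an assumption and is shown over a range.

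- Enrolment product = 100 × (1 − s)
- cPR cut-off = 50, a 50% fall from 100
- On-study change needed = 50 / [100 × (1 − s)] − 1

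| s | Enrolment product | On-study change needed for cPR |
|---|---|---|
| 0% | 100 | −50% |
| 10% | 90 | −44.4% |
| 20% | 80 | −37.5% |
| 30% | 70 | −28.6% |
| 40% | 60 | −16.7% |
| 50% | 50 | 0% |
| 60% | 40 | up to +25% still qualifies |
| 70% | 30 | up to +66.7% still qualifies |

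Overlap with cPD: at s = 60%, growth of 25% gives 40 × 1.25 = 50, which is exactly a 50% fall from 100. The mass meets cPR and, if the cPD reference is the study baseline, cPD as well. At s = 70%, 30 × 1.25 = 37.5, and both are again met.

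Illustration in centimetres (assumed sizes): 6 × 6 = 36 before chemotherapy, then 4 × 4 = 16 on day 1 and still 16 on study. The fall is 1 − 16/36 = 55.6%, so the patient is a cPR with no change on study.

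**3. Reach**

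With the maximum of 41 patients in Section 12.2, each misclassified patient moves the response rate by 1/41 = 2.4 percentage points. With the minimum of 12 it is 1/12 = 8.3 points. The documents do not say how many second-cohort patients are expected, or how many will have palpable breast disease.

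The primary response in 12.1 uses Ki67 with ER, or pathologic complete response, so clinical response does not enter it. As a context check, the Simon design (12 then 32 patients; continue with at least 1 response, promising with at least 4) was recomputed exactly. Early stopping is 0.540 at a true rate of 5% and 0.069 at 20%. The probability of a promising result is 0.065 and 0.866 respectively. These agree with the plan's 0.54, 0.07, 0.07 and 0.87, and none depends on 11.2.1.

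**The case against.** A reader might infer that the reference fails in both cohorts. The documents do not support that. First-cohort patients are chemotherapy-naive, a decrease needs an earlier reference, and Section 11.2 supplies the obvious one at enrolment. The term fails to single out that examination, but no earlier chemotherapy shrinkage exists to be miscounted.

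The second-cohort bias can also be challenged:

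- **No such data are scheduled.** Sections 4.2, 10 and 10.1 record tumour size only from screening onward. A site would need an outside record of the same mass. This stands: the bias is conditional, and many sites would probably use enrolment. But in a multi-centre study with any treating investigator or designee examining, an undefined term invites differing practice. A rule that cannot be applied from study data needs correcting anyway.
- **The criteria may not be meant for this cohort.** Objective 3 speaks of preoperative treatment, Section 11 of re-evaluation until surgery, and 11.2.1 of palpable breast disease; the second cohort has restaging scans. This stands in part. Section 12.4 nevertheless includes all eligible patients, and no imaging response criteria are given in place of palpation.
- **Different words need not mean different starting points.** True. The overlap of cPR and cPD holds only if the cPD reference is the study baseline.
- **It is a secondary endpoint.** True, and it limits the weight of the point.

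**Conclusion.** The point holds as a faulty reference in a secondary endpoint definition. In the first cohort it is imprecise wording with no carry-over bias. In the second cohort, the rule as written points before study entry and lowers the on-study change needed for cPR from a 50% fall to 28.6% at 30% prior shrinkage and to none at 50%. At 60% or more, a mass growing 25% on study can still qualify.

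This rests on three assumptions: that a prechemotherapy size is obtained and used, that the patient has palpable breast disease measurable in two dimensions, and that prior shrinkage is in the range shown. It would be wrong to conclude that misclassification is certain or that the trial's main decision is compromised. Only secondary objective 3 is affected; sample size, stopping rule and primary response are unchanged. The correction should be made.

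**What to change.** For endpoint scoring in 11.2.1, replace both references with one: the last tumour measurement before the first dose of entinostat. That is the day 1 measurement, or the screening examination where day 1 is waived under 10.3. The fall needed for cPR is then 50% in every patient, whatever happened before enrolment.

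State in 11.2.1 and 12.4 whether the palpation criteria apply to the second cohort.

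Two related items need separate reconciliation. The first is any use of cPD for the second cohort's rule of treating until progression; the change proposed here concerns scoring only. The second is the conflict between 3.1.7, which bars prior chemotherapy as a general criterion, and 3.1.16, which requires it.

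The reference change costs one line of wording plus the scope statement. The measurement is already scheduled, and no sample size or power figure changes. The downside is a possibly lower cPR rate.
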